## **Intervention Arm (IA) program**

### *-Dietary caloric-protein restriction*

Patients randomized in the IA will be given individualized dietary advice on the basis of WCRF/AICR recommendations.[6,38] The aim of healthy dietary advice will be the reduction of patient's total daily calorie intake up to 600 kcal below their energy requirements. Energy requirement for each patient in the IA will be estimated through revised Harris-Benedict formula,[62] which combines basal metabolic rate (BMR) and physical activity level. In addition to caloric restriction, dietary intervention will aim for a total protein intake to 0.8g of protein/Kg body weight mostly from plant-origin food.

Patients will be required to keep a weekly diet diary that will be analyzed with metaDieta 3.5 software (Me.Te.Da. s.r.l., San Benedetto del Tronto, Ascoli Piceno, Italy). Once a month for the first four months and bi-monthly for the rest of intervention period, patients will meet individually with the dietitian for a 45-minute nutritional counselling session. During these meetings, patients will discuss their diet diary with the dietitian in order to identify the best strategy to comply with the caloric restriction program.

*-Health coaching*

After the nutritional counseling session with the dietitian, patients in the IA will meet with a trained nurse (coach) for a 15-minute health coaching session. During these sessions, the role of the coach will be to empower participants to take control of their own health, to move the attention from what professionals want to the patient's own objectives, to help patients to achieve their objectives through feasible steps, and to challenge behaviors that represent an obstacle to positive change.

*-Cooking classes*

Each patient in the IA will be involved in at least three 4-hour sessions of culinary practice (cooking classes). Participants will be asked to take part to the cooking classes with a relative, such as a wife or husband.

The aim of this practical part of the intervention will be to provide patients with skills and knowledge that they will be able to use to modify their dietary approach and behaviors, and to reach the goal of calorie restriction. Every session and every recipes will be developed based on the Mediterranean Diet in accordance with WCRF/AICR recommendations and with the Healthy Eating Plate proposed by the Harvard School of Public Health using healthy, mostly local and seasonal foods.[6,38,63] Cooking classes will be held by a dietitian and professional cook. At the end of each cooking class, participants will have lunch together, consuming the meal they prepared, and they will discuss the learned knowledge with the dietitian.

*-Physical activity*

Patients in the IA, after a medical/cardiac evaluation to assure their physical ability for exercise, will attend Nordic walking sessions of moderate intensity two times per month during the 24 months of intervention. A certified expert will supervise every Nordic walking session.

Patients will be also counselled on how they can perform physical activity of moderate-intensity by themselves or in a group in their usual living environment.

Participants in the IA will be provided with a pedometer (Omron walking style IV, Omron Healthcare Europe B.V.) to check the number of steps or distance (Km) walked each day.

Nordic walking session will be performed in groups of twelve participants. Every session will start with 10-minutes of warm-up exercises and will continue with moderate intensity walking in a green, pedestrian area.

Patients will be encouraged to maintain a good level of physical activity during the rest of the week, with 40 minute of brisk walking 4 days/week.

All patients in the IA will receive reminders, of their appointments for nutritional counseling, cooking classes and Nordic walking sessions, through phone call, e-mail or/and text message on their mobile phone and will be contacted for any change in the scheduled activities due to unexpected events, for example bad weather in the case of Nordic walking.

## **Control Arm (CA) program**

Participants in the CA will be given information about the importance of a healthy lifestyle in reducing the risk of cancer and will receive a leaflet based on WCRF/AICR recommendations.[38]

## Statistical analysis

Fisher's exact test will be used for comparison of categorical variables. Numerical variables will be expressed as median and interquartile range (Q1; Q3). The Mann-Whitney *U*-test will be used to evaluate differences between IA and CA groups. Paired Student's T test will be used to compare the difference in the parameters measured at baseline (at the time of enrolment) and at the end of the trial in the same patient. Spearman's rank correlation coefficient will be calculated to evaluate the correlation between two measured parameters. All tests will be two-tailed and a *p* value lower than 0.05 will be assumed to indicate a significant difference. Data analyses will be performed with SPSS v20 and Stats-Direct.

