At the time of enrollment, anthropometric and body composition measurements will be recorded for each patient and they will be allocated by a data manager in the IA or CA. Blood samples will be obtained from each patient and blood glucose will be determined. Serum metabolic biomarkers will be measured in each serum sample and total proteins will be extracted from fresh frozen esophageal biopsy and will be analyzed to evaluate the insulin signal pathway.

To assess esophageal microbiota profiling, total gDNA will be extracted from matched fresh frozen biopsy. In order to determine a score of adherence to cancer prevention recommendations, participants will be asked to complete a self-administrated questionnaire reflecting WCRF/AICR recommendations. Measurements will occur also at the end point, after two years from the enrollment.

**Ethics and dissemination:** Ethical approval for the study has been received from the Ethics Committee for Clinical Experimentation (Comitato Etico per la Sperimentazione Clinica – CESC) of the Veneto Institute of Oncology (approval number CESC IOV2015/68). This randomised controlled trial will generate substantial information regarding the effect of multimodal approach to reduce

risk of esophageal adenocarcinoma in high-risk population. The results of the study will be disseminated through publication, reports and conference presentation.

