## OBJECTIVES

In this study, patients are randomly divided into two arms, a control arm and an interventional arm. The aim of this two-arms randomized clinical trial is to assess the effect of a moderate CALoric-protein REstriction PROgram (CARE-PRO) on metabolic-hormonal condition (such as excessive BMI and/or waist circumference (WC), insulin resistance, unbalanced esophageal microbiota composition, chronic inflammation and adipose tissue-related hormones release) which can represent, when altered, a risk factor for the development of esophageal adenocarcinoma in patients with Barrett's esophagus. The control arm receives information about a correct lifestyle

and suggestions to increase the consumption of fiber and vegetable proteins. The interventional arm instead is involved in the two-year program of moderate caloric and protein restriction.

*-Overall aim of the study*

The main objective of the study is to evaluate the impact of a lifestyle-oriented (diet, physical activity, behavior change) intervention on body weight, waist circumference, biomarkers associated with cancer risk, esophageal microbiota composition and adherence to cancer prevention recommendations (WCRF/ARICR 2007) after 24 months in overweight or obese ( $BMI \geq 25.0 \text{ Kg/m}^2$ ) BE patients.

*-Primary aim*

To examine the effect of a dietary and exercise intervention on body weight and waist circumference reduction in overweight or obese BE patients.

*-Secondary aims*

To assess the impact of CARE-PRO intervention on the relationship between anthropometric parameters (body weight, BMI and WC), metabolic serum biomarkers, the expression of proteins involved on insulin and IGF1 receptors signal transduction and esophageal microbiota composition associated with an increased risk of developing EAC.

- i) To assess the impact of CARE-PRO intervention on the adherence to WCRF/AICR recommendations for cancer prevention.[6,38] Adherence to cancer prevention recommendations will be assessed by a validated score of adherence.[39]
- ii) To evaluate possible differences on CARE-PRO outcomes between elderly ( $> 65$  years) BE patients and younger BE patients ( $<65$  years).
- iii) To evaluate economic costs of the intervention.

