### *-Sample size*

The sample size is based on the primary outcome of a clinically significant change in body weight at the end of the study. A 7% weight loss has been shown to be clinically effective in reducing the risk of diabetes. According to previous data,[44] it is expected that around 30% of patients enrolled in the IA and 15% of those enrolled in the CA will achieve the aforementioned weight loss within the time allotted for trial. In order to reveal a statistically significant difference in the rates of achievement of a 7% weight loss between IA and CA, at least 95 patients are required for each group (power: 80%, type-1 error: 5%). In order to achieve this sample size, we estimate that a pool of 340 patients will be required for recruitment, to allow a recruitment rate of 70% (n=238), and a subsequent drop-out rate of 20% (n=190).

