### *-Randomization*

At the time of enrollment, prior to group allocation, anthropometric and body composition measurements (such as height, body weight, waist circumference at the umbilical level, BMI [weight/(height) (Kg/m^2) will be recorded for each patient immediately before endoscopic procedure. Patients will be randomly allocated by a data manager in the intervention (IA) or control arm (CA), using a permuted-block technique, with block size of four or eight. The Data Manager will not be involved in recruitment or intervention process.

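### Numerical outcomes are compared between arms only by an unadjusted Mann-Whitney test on an unnamed value, with no between-arm effect or confidence interval planned

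*Combined protocol and SAP*

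**What the plan says.** The Statistical analysis section of the combined protocol and SAP is one paragraph. For numerical variables it provides:

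- a summary by median and quartiles;
- one comparison of the arms, the Mann-Whitney test, which "will be used to evaluate differences between IA and CA groups";
- a paired t-test, with this stated purpose: "compare the difference in the parameters measured at baseline (at the time of enrolment) and at the end of the trial in the same patient";
- correlations between pairs of measurements, by Spearman's method.

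Categorical variables go to Fisher's exact test. All tests are two-tailed at 0.05. No regression model, covariate adjustment, between-arm estimate or confidence interval appears anywhere in the document.

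Under Objectives, the primary aim is the effect of the intervention "on body weight and waist circumference reduction in overweight or obese BE patients". The Sample size section bases the trial on a "clinically significant change in body weight at the end of the study", made binary as a 7% weight loss. The data for adjustment will exist. Under Randomization, anthropometry is taken before allocation and "will be recorded for each patient immediately before endoscopic procedure". The Abstract adds: "Measurements will occur also at the end point, after two years from the enrollment".

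**The concern.** Three gaps follow from that paragraph.

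1. **The tested variable is not named.** It could be the 24-month value, the absolute change or the percentage change. Two analysts could follow the plan and run different tests, and the choice could be made after the data are seen.
2. **No between-arm effect is planned.** The report would hold medians per arm and p values, with no difference in kg, cm or biomarker units and no statement of its uncertainty. Waist has no responder definition, so that half of the primary aim rests entirely on this test.
3. **Baseline is not used between arms.** The only sentence that mentions it is the paired t-test, which works within patients and does not compare IA with CA.

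At stake are the size and precision of the answer to the primary aim, and of the serum biomarker, HOMA-IR and adherence-score comparisons.

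**Working it through.** **Inputs from the documents.** 95 patients per arm; 30% v 15% reaching 7% weight loss (Sample size); two-tailed 5% (Statistical analysis).

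**Assumptions.** The documents give no SD, distribution or baseline-to-24-month correlation r. I take r = 0.5 to 0.9 and equal SDs at both times, and treat percentage change like absolute change.

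**Step 1: the plan's own figure.** With a pooled variance, n = [z_α √(2·0.225·0.775) + 0.842 √(0.30·0.70 + 0.15·0.85)]² / 0.15². One-sided 5% gives 95 per arm; two-sided gives 121. The stated 95 is therefore a one-sided figure. That is a separate matter about the binary outcome, and 95 is used below only as the group size.

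**Step 2: the effect implied for weight change.** The plan expects "around 30% of patients enrolled in the IA and 15% of those enrolled in the CA will achieve the aforementioned weight loss". If change is normal with equal SDs, the shift is z(0.30) − z(0.15) = −0.524 + 1.036 = 0.512 SD of change.

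**Step 3: variances under normality**, in units of the outcome variance: 24-month value 1; change 2(1 − r); ANCOVA 1 − r². The Mann-Whitney test has relative efficiency 3/π = 0.955. Hence 95 per arm by Mann-Whitney on change is worth 95 / [(2/(1 + r))·(π/3)] per arm by ANCOVA: 68, 77 and 86 for r = 0.5, 0.7 and 0.9.

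**Step 4: power under normality.**
- Mann-Whitney on change at 0.512 SD: 0.512·√(95·0.955/2) = 3.45, and Φ(3.45 − 1.96) = 93% at every r.
- ANCOVA at r = 0.5: 0.512·√(2/1.5)·√(95/2) = 4.07, and Φ(4.07 − 1.96) = 98%.
- Where ANCOVA has 80%, the difference is 2.80·√(2(1 − r²)/95) outcome SDs, that is 0.352, 0.290 and 0.177.

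| | r = 0.5 | r = 0.7 | r = 0.9 |
|---|---|---|---|
| ANCOVA, implied weight effect | 98% | 97% | 95% |
| Mann-Whitney on change, same effect | 93% | 93% | 93% |
| Mann-Whitney on change where ANCOVA has 80% | 66% | 71% | 76% |
| Width of Hodges-Lehmann CI on change ÷ ANCOVA CI | 1.18 | 1.11 | 1.05 |

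Simulation (20,000 trials per setting; 1,500 for the interval widths) gives the same picture.

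**Step 5: without normality.** Symmetric heavy-tailed residuals with the same variance, ANCOVA held near 80%, 4,000 trials per setting; Mann-Whitney on change v ANCOVA:

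| Residuals | r = 0.5 | r = 0.7 | r = 0.9 |
|---|---|---|---|
| t, 5 df | 73 v 80% | 79 v 80% | 84 v 80% |
| t, 4 df | 77 v 81% | 82 v 81% | 89 v 81% |
| Laplace | 75 v 81% | 81 v 80% | 88 v 80% |

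ANCOVA leads at 0.5, the two are about level at 0.7, and Mann-Whitney leads at 0.9. Steps 3 and 4 therefore hold only under normality.

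**Step 6: adjustment apart from the choice of test.** If the rank test is kept but applied to baseline-adjusted residuals, power was higher than on change in every normal and heavy-tailed setting (78–92% against 67–89%). Using baseline helps even where ANCOVA itself does not win.

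**Step 7: adherence score** (0 to 6 in half-points; assumed mean 3–5, SD 0.8–1.2, r 0.5–0.9; 18 settings). ANCOVA power was 64–79% against 55–70% for Mann-Whitney on change, higher by 4–18 points in every setting. Type I error was 4.6–5.2% and 4.6–5.7%.

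**The case against.** The strongest reply is that the authors chose medians, quartiles and a rank test, which suits outcomes not presumed normal, and that the precision case for ANCOVA depends on normality. This stands. Step 5 shows that even the direction of the difference is unknown without the distribution and r, and a log transform deals with skew but not with symmetric heavy tails. It does not rescue the plan, because naming the tested variable and giving an effect with its interval are needed whichever test is used.

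Second, the loss for weight is small even under normality: 2 to 5 points at the one effect the protocol implies. This also stands. The 66–76% figures use an effect set so that ANCOVA has 80%; no document figure supports that size for any outcome.

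Third, a reader might infer that raw 24-month values will be tested, with power at the implied weight effect of about 93%, 75% or 33% (r = 0.5, 0.7, 0.9). The documents do not say so. The primary aim speaks of reduction and the Sample size section of change, so change is the more natural reading. Those figures show why the variable should be named, but they should not set the weight of this point.

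Fourth, a rule for every numerical outcome would be too broad. Tissue signalling proteins and 16S profiles are numerical too, and taxon abundances can contain zeros, for which a plain log fails. This is accepted, and they are left out of the fix.

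**Conclusion.** The point holds as a gap in specification and reporting. The between-arm analysis of numerical outcomes names no tested variable, does not use the collected baseline, and yields no effect estimate with an interval for an aim that is stated as an effect.

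Two stronger readings are not supported. One is that the p values are biased or the error rate inflated: Mann-Whitney is a valid comparison of randomised arms on either variable. The other is that the outcome on which the trial is sized is compromised: the 7% responder outcome already uses baseline weight and falls under Fisher's exact test.

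The precision cost is small for weight and moderate for smaller effects, under normality and r of 0.5 to 0.9; with heavy tails it can vanish or reverse. The weight effect is the only one the documents allow to be derived; they give nothing comparable for waist or biomarkers. The missing estimate and the unnamed variable do not depend on these assumptions. The change should be made, but the trial's validity does not hang on it.

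**What to change.** Add to the Statistical analysis section, before any unblinded analysis:

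- For body weight, waist circumference, serum biomarkers, HOMA-IR and the adherence score, the between-arm effect at 24 months will be estimated by ANCOVA, with the 24-month value regressed on arm and baseline value. It will be reported as an adjusted difference, or a ratio for log-transformed outcomes, with 95% CI. The outcomes to be log-transformed will be listed by name before unblinding.
- Mann-Whitney on change from baseline, with the Hodges-Lehmann shift and its 95% CI, will be a sensitivity analysis.
- Within-arm paired t-tests will be labelled descriptive.
- Fisher's exact test stays for the 7% responder outcome.
- Tissue signalling and 16S microbiota measurements are outside this rule.

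If the team prefers a rank-based main analysis, the minimum is to name change from baseline as the tested variable and report the Hodges-Lehmann shift with its 95% CI. Under normality that interval would be about 5–18% wider than the ANCOVA interval.

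The cost is analysis wording only. Baseline and two-year values are already collected, so no new visits or data are needed.

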### *-Serum analysis*

Serum metabolic biomarkers such as fasting glucose (mg/dl) insulin (pg/ml), C-peptide (pg/ml), IGF1 (nmol/ml) and its binding proteins IGFBP1 (nmol/ml) and IGFBP3 (nmol/ml), leptin (ng/ml), adiponectin (μg/ml), TNF-alpha (pg/ml) and IL-6 (pg/ml) levels will be measured in each serum sample with Luminex xMAP® technology (multiplexed fluorescent bead-based immunoassay, Luminex, TX, USA); insulin resistance index (HOMA-IR index) will be calculated using the formula: [fasting plasma glucose (mg/dl) × fasting serum insulin(μU/ml)/405], according to the method developed by Matthews et al.[60] HOMA-IR index  $\geq 2.5$  will be selected as cut-off for insulin-resistance according to Capasso et al.[61]

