### *-Esophageal biopsy analysis: Insulin/IGF1 signal transduction and microbiota composition*

Total proteins will be extracted from fresh frozen esophageal biopsy and will be quantified by Bicinchoninic Acid (BCA) assay (Thermo Scientific Pierce, IL, USA). For each sample, 12.5 μg of total proteins will be analyzed to evaluate the activation state of Insulin Receptor (IR) and IGF1 Receptor (IGF1R) signal pathways using Luminex xMAP® technology. Both the metabolic PI3K/Akt pathway and the mitogenic (ERK/MAPK) pathway will be analyzed.

To assess esophageal microbiota profiling, total gDNA will be extracted from fresh frozen biopsy. Specific primers for the bacterial V3-V4 hypervariable regions of 16S rRNA will be used to amplify bacterial DNA [ $\approx$  500 bases pair (bp)] to be sequenced by Illumina MiSeq platform with 300 bp paired-end approach. BMR Genomics (Padua, Italy) will perform the sequencing.

Biopsy and serum samples stored in nitrogen will, as a routine, be managed by the Biological Bank staff who will provide for their conservation in a totally anonymity (as prescribed by law and already authorized by the Ethics Committee with prot. No. P 480 2002)

The acceptance or rejection by patients to participate in the study will not change in any way their established diagnostic-therapeutic procedures and follow-up.

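### No multiplicity control for the biomarker and microbiota tests: up to about a 43% chance of a false positive in the serum panel alone, and more as further tests are added

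*Combined protocol and SAP*

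**What the plan says.** The Statistical analysis section names Fisher's exact test for categorical variables and three methods for numerical ones:

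- Between arms, the Mann-Whitney "test will be used to evaluate differences between IA and CA groups".
- Within patients, a paired t test "will be used to compare the difference in the parameters measured at baseline" and at the end of the trial.
- For association, Spearman's "rank correlation coefficient will be calculated to evaluate the correlation between two measured parameters".

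One decision rule covers all of them: "All tests will be two-tailed", and a p "value lower than 0.05 will be assumed to indicate a significant difference". Neither this section nor any other gives a multiplicity adjustment, a false-discovery method, an order of testing or an exploratory label.

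The measurements to which the rule would apply are spread over two sections. The Serum analysis section lists ten analytes, whose "levels will be measured in each serum sample with Luminex xMAP", and adds HOMA-IR. The list is introduced by way of example, so it is not closed. The Esophageal biopsy analysis section adds signalling proteins in the PI3K/Akt and ERK/MAPK pathways, without a count. It also adds 16S sequencing: "To assess esophageal microbiota profiling, total gDNA will be extracted from fresh frozen biopsy". No taxonomic level, list of taxa or microbiota-specific test is given.

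**The concern.** Under a single unadjusted threshold, the chance that at least one biomarker result is called significant by luck grows with each test. Here the number of tests is both sizeable and open.

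The outcomes affected are not peripheral. The Objectives section ranks serum markers, pathway proteins and microbiota as secondary. However, the abstract includes biomarkers and microbiota in its primary aim, and the overall aim in Objectives includes them as well. The Translational relevance section would base a proposal of the programme as a therapy on efficacy for body weight together with changes in risk biomarkers, and it looks ahead to fewer surveillance endoscopies. The biomarker half of that argument would rest on unadjusted tests drawn from a list that is not fixed.

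**Working it through.** **The plan's own figure.** The documents state no family-wise or false-discovery rate. The only stated type-1 error is the 5% in the Sample size section (30% versus 15%, 80% power, 95 per group). With n = [z_a·√(2·p̄·q̄) + z_b·√(p1·q1 + p2·q2)]² / (p1 − p2)² and p̄ = 0.225:

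- One-sided 5%: (1.645 × 0.5906 + 0.8416 × 0.5809)² / 0.0225 gives 95, the stated figure.
- Two-sided 5%: (1.960 × 0.5906 + 0.8416 × 0.5809)² / 0.0225 gives 121.

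So 95 per group matches a one-sided test, although the analysis section makes all tests two-tailed. At 95 per group the two-sided power is 70%, or about 65% with Fisher's exact test. This is a separate matter, but it bears on the fix.

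**Count of serum measures.** Glucose, insulin, C-peptide, IGF1, IGFBP1, IGFBP3, leptin, adiponectin, TNF-alpha and IL-6 make 10. HOMA-IR makes 11.

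**Chance of at least one false positive, all nulls true.** For k independent tests at 0.05 it is 1 − 0.95^k, and the expected number of false positives is 0.05k. For correlated tests, the figures come from simulating equally correlated two-sided normal tests (40,000 runs). The correlations are assumptions; the documents give none.

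| Tests | Independent | Correlation 0.3 | Correlation 0.5 |
|---|---|---|---|
| 11 (serum, between arms) | 43% | 38% | 30% |
| 21 (serum plus the 10 genera named in the Introduction) | 66% | 56% | 43% |
| 61 (serum plus an assumed 50 taxa or proteins) | 96% | 85% | 67% |

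Only the first row uses a count taken from the plan's list of measurements. The second is a low scenario, because the plan does not say that those genera will be tested. The third is purely an assumption.

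The expected number of false positives for the 11 serum tests is 0.05 × 11 = 0.55, whatever the correlation.

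**Favourable direction only.** A two-tailed test at 0.05 puts 0.025 in each tail, so for 11 independent tests the chance is 1 − 0.975^11 = 24%.

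**Tests needed for near-certainty.** ln(0.05) / ln(0.95) = 58.4, so about 59 independent null tests are needed to reach 95%.

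**Adding the other planned methods.** Suppose the serum panel is tested between arms (11), by paired t test in each arm (22) and by Spearman against weight, BMI and waist circumference (3 × 11 = 33). The count is then 66, and 1 − 0.95^66 = 96.6%. That figure cannot be used as an estimate. The 66 tests share the same data, so they are not independent, and several would be expected to be non-null on the protocol's own rationale. It shows only that the number of tests grows quickly.

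**The case against.** A reader might infer that false biomarker or microbiota findings are close to certain. The documents do not support this. The one panel that can be counted gives 43% at most, which is below even odds. Near-certainty depends on a number of taxa and proteins that the plan does not state, and on testing taxa one by one, which it does not announce. The Introduction frames the microbiota as two types and the Objectives speak of composition, so the analysis could be one or a few tests. Correlation lowers the figures further; HOMA-IR, for example, is computed from glucose and insulin. Correlations of anthropometry with metabolic markers are expected to be real, so they should not all be counted as potential false positives.

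A reader might also infer that one chance biomarker result would be enough for an inert programme to be proposed as therapy. The Translational relevance section asks for a body-weight effect and biomarker changes together, and it does not name the microbiota. Only a favourable shift would help the case, hence the 24% figure.

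It can also be said that secondary outcomes are commonly read as exploratory. That would be an answer if the plan said so. It does not: its rule calls any nominal p below 0.05 a significant difference, and the abstract lists these outcomes in the primary aim.

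The first two objections limit the size and reach of the problem. They do not remove it.

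**Conclusion.** The concern holds in a limited form. The plan has a stated significance rule with no multiplicity control and no exploratory label, applied to a list of tests that is not fixed. If the programme has no effect on the 11 serum measures, the chance of at least one false positive between arms is up to about 43% under independence and about 30% at an assumed correlation of 0.5. It is about 24% under independence for a false positive in the favourable direction. The chance rises with proteins, correlations and any taxon-level tests, but how far cannot be computed from the documents. All these figures assume that every null is true; measures that truly change reduce the number of possible false positives.

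The weight-loss comparison that sizes the trial is not undermined by this. What is weakened is the biomarker part of the argument for the programme, and any microbiota claim. The point is worth acting on because the remedy is cheap.

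**What to change.** Before analysis, amend the Statistical analysis section as follows.

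1. **One primary test.** Designate the 7% weight-loss responder comparison from the Sample size section as the single primary test at two-sided 0.05. The primary aim also names waist circumference; make it secondary, or test it in a fixed order after weight. This does not repair the power shortfall shown above, which needs its own answer.
2. **Listed families.** List the secondary between-arm tests by family: serum markers with HOMA-IR; pathway proteins; microbiota, including taxa if they are tested individually. Give the adherence score an explicit place as well, since it is a secondary aim.
3. **Control within families.** Apply Benjamini-Hochberg at a 5% false discovery rate within each family. Report adjusted p values with between-arm effect estimates and confidence intervals.
4. **Exploratory in advance.** Label the correlations, the age-group comparison and any unlisted test exploratory, whatever the result. Paired within-patient tests fall here unless listed.

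If every null in a family is true, this holds the chance of any false positive in that family to 5% under independence or positive dependence. It does not control error across families: three independent families could give up to 1 − 0.95³ = 14%.

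The cost is plan wording and one routine calculation, with no new data or patients. The downside is fewer nominally significant secondary results. In addition, the leading secondary aim is worded in terms of relationships between measures, so if the correlations are meant to carry weight, they must be listed as a family of their own.
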